7.1 Specification of Safety Parameters

7.1.1 Unanticipated Problems

The Office for Human Research Protections (OHRP) considers unanticipated problems involving risks to subjects or others to include, in general, any incident, experience, or outcome that meets **all** of the following criteria:

- unexpected in terms of nature, severity, or frequency given (a) the research procedures that are described in the protocol-related documents, such as the IRB-approved research protocol and informed consent document; and (b) the characteristics of the subject population being studied;
- related or possibly related to participation in the research ("possibly related" means there is a reasonable possibility that the incident, experience, or outcome may have been caused by the procedures involved in the research); and
- suggests that the research places subjects or others at a greater risk of harm (including physical, psychological, economic, or social harm) than was previously known or recognized.

7.1.2 Adverse Events

An adverse event is any untoward or unfavorable medical occurrence in a human subject, including any abnormal sign (for example, abnormal physical exam or laboratory finding), symptom, or disease, temporally associated with the subject's participation in the research, whether or not considered related to the subject's participation in the research.

7.1.3 Serious Adverse Events

A serious adverse event (SAE) is one that meets one or more of the following criteria:

- Results in death
- Is life-threatening (places the subject at immediate risk of death from the event as it occurred)
- Results in inpatient hospitalization or prolongation of existing hospitalization
- Results in a persistent or significant disability or incapacity

7.2 Characteristics of an Adverse Event

7.2.1 Relationship to Study Intervention

To assess relationship of an event to study intervention, the following guidelines are used:

- 1. Related (Possible, Probable, Definite)
 - a. The event is known to occur with the study intervention.
 - b. There is a temporal relationship between the intervention and event onset.
 - c. The event abates when the intervention is discontinued.
- 2. Not Related (Unlikely, Not Related)
 - a. There is no temporal relationship between the intervention and event onset.
 - b. An alternate etiology has been established.

7.2.2 Expectedness of SAEs

The Study PI will be responsible for determining whether an SAE is expected or unexpected. An adverse event will be considered unexpected if the nature, severity, or frequency of the event is not consistent with the risk information previously described for the intervention.

7.2.3 Severity of Event

The following scale will be used to grade adverse events:

- 1. Mild: no intervention required; no impact on activities of daily living (ADL)
- 2. Moderate: minimal, local, or non-invasive intervention indicated; moderate impact on ADL
- 3. Severe: significant symptoms requiring invasive intervention; subject seeks medical attention, needs major assistance with ADL

7.3 Reporting Procedures

7.3.1 Unanticipated Problem Reporting to IRB and NIDA

Incidents or events that meet the OHRP criteria for unanticipated problems require the creation and completion of an unanticipated problem report form. OHRP recommends that investigators include the following information when reporting an adverse event, or any other incident, experience, or outcome as an unanticipated problem to the IRB:

- appropriate identifying information for the research protocol, such as the title, investigator's name, and the IRB project number;
- a detailed description of the adverse event, incident, experience, or outcome;
- an explanation of the basis for determining that the adverse event, incident, experience, or outcome represents an unanticipated problem;
- a description of any changes to the protocol or other corrective actions that have been taken or are proposed in response to the unanticipated problem.

To satisfy the requirement for prompt reporting, unanticipated problems will be reported using the following timeline:

- Unanticipated problems that are serious adverse events will be reported to the IRB and to NIDA within 1 week of the investigator becoming aware of the event.
- Any other unanticipated problem will be reported to the IRB and to NIDA within 2 weeks of the investigator becoming aware of the problem.
- All unanticipated problems should be reported to appropriate institutional officials (as required by an institution's written reporting procedures), the supporting agency head (or designee), and OHRP within one month of the IRB's receipt of the report of the problem from the investigator.

7.3.2 Serious Adverse Event Reporting to NIDA

Procedures and timeline for reporting AEs to NIDA.

AEs will be reported to the NIDA PO at least once per year as a part of the annual progress report. These reports will describe the event, when it occurred, the study arm of the participant, and the outcome/resolution. If there are no AEs in a given year, the report will include a statement to this effect.

Procedures and timeline for reporting SAEs to NIDA.

SAEs, whether or not anticipated, will be reported to the NIDA PO within 24 hours of the event by email. This 24 hour notification will include a brief explanation of the SAE and when it occurred. A written follow up will be sent within 72 hours of the event. This written follow up will include information on the date of the event, what occurred, actions taken by project staff, planned follow up (if any), the intervention group/study arm of the affected participant, whether the event appears to be related to the intervention, and whether participant will continue in the study.

Reporting of IRB actions to NIDA.

Follow-up reports to the NIDA program official—made within 48 hours of IRB actions will specify IRB actions related to study shut-down or changes. We will follow Wayne State University policy in the handling of all AEs and SAEs; see Appendix 1 for algorithm from the WSU IRB, which will be followed in all respects except with regard to unanticipated SAEs, which will be reported to NIDA.

Wayne State University Risk-Adverse Event Algorithm:

Problems Involving Risk- Adverse Event Algorithm

8 STUDY OVERSIGHT

In addition to the PI's responsibility for oversight, this study will use a DSMB to be consistent with a Financial Conflict of Interest (FCOI) management plan from Wayne State University, resulting from the PI's part ownership of the company that markets the software intervention authoring tool that will be used in this study. (Other elements of this management plan include ensuring that the PI's grants are never charged for use of the software, disclosing the potential COI on all publications and presentations, and noting the potential COI in consent documents.) Members of the DSMB assembled for this study include:

- i. [name], University of Cincinnati School of Medicine. [name] has conducted multiple NIH-funded clinical trials, many under the auspices of NIDA's Clinical Trials Network, and one of which was a study seeking to reduce drug use among pregnant women.
- ii. [name], Wayne State University School of Medicine. [name] has led or been part of multiple NIH-funded clinical trials for smoking or gambling, and as a clinician supervises treatment of opioid-dependent pregnant women.
- iii. [name], Harvard University Medical School/VA Boston Healthcare System. [name] is a leader in brief intervention trials for alcohol use in pregnancy.

Charge of the Board DSMB (e.g., advising PI, sending report to IRB, etc.). The DSMB will review all aspects of the study, including recruitment rate, randomization, AEs, protocol violations, unexpected events, etc., and will advise the PI in terms of maintaining participant safety and confidentiality. They will also be asked to verify that study conduct is not influenced by any potential FCOI. They will be asked to approve a report to be sent to the IRB and to NIDA.

Statement of no conflicts of interest. All DSMB members will sign a form verifying that they have no conflicts of interest with respect to the proposed study. None of the DSMB members are involved in any way in carrying out this study.

Frequency of meetings. The DSMB will receive reports and meet at least annually. Additional meetings may be called, as needed, to respond to SAEs or any other study-related challenges.

PI acknowledgement of requirement to report DSMB activity as part of Annual Progress Report to NIDA. All DSMB activity will be reported to NIDA as part of the annual progress report, as required.

In addition to being made aware of possible risks during the informed consent process, participants will be protected against these potential risks in a number of ways. As noted in the Human Subjects section of this application, we will not collect information about drug use during pregnancy (other than for participants in the cross-validation subsample, whose data in this regard will be anonymous and unavailable until after the participant has left the hospital). Further, we have sought and obtained a Federal Certificate of Confidentiality, and will utilize ACASI technology which makes the RA blind as to all participant data.

9 STATISTI CAL CONSIDERATIONS

9.1 Stud y Hypotheses

Data analysis will seek to (1) verify intervention feasibility and acceptability, (2) obtain preliminary efficacy estimates as measured by confirmed self-report (as recommended by an expert panel convened by NIDA; Donovan et al., 2012); and (3) also measure efficacy in terms of a quantitative measure of drug using days. Details on these three analytic elements are provided below. All significance tests will follow standard procedures for evaluating distributional assumptions, disproportionate or biased followup, and randomization success, and will utilize transformations and replacement of missing data using multiple imputation as appropriate. Manuscripts based on these results will be written and submitted during quarter 12 (the end of project year three). This work will form the basis of the R01/Stage II study application to follow, *unless* the results suggest that more Stage 1 work is needed before proceeding to a fully powered trial. We see the proposed Stage 1 project as a true test of whether these approaches, alone or in combination, merit further evaluation.

Feasibility will be demonstrated if a high proportion of participants receive the intervention as intended, and **acceptability** will be demonstrated if participant ratings show a high degree of satisfaction and usability. *Hypothesis 1a:* 90% or more of participants assigned to the eSBIRT conditions will successfully complete the intervention at the same clinic visit at which they are recruited. *Hypothesis 1b:* 90% or more of participants assigned to the tailored texting conditions will report receiving and reading at least five text messages. *Hypothesis 1c:* Based on prior standards (e.g., Ondersma et al., 2013), we predict that participants assigned to the intervention conditions will rate them as highly acceptable, helpful, and easy to use (mean of \geq 4.5 on a 1-5 scale ranging from "not at all" to "very much").

9.2 Sample Size Considerations

Power is neither required nor expected to be adequate in Stage I pilot trials. In an exploratory power analysis, we show power of 0.8 to detect a medium to large effect (d = 0.69), which we do not expect. We do expect the strongest effects to be between the combined intervention and the control group.

Days of marijuana use in the past 90 days (per timeline follow-back interview) will be the third efficacy-related primary outcome of the pilot trial. To assess changes in days of marijuana use, generalized linear models using a Poisson loglinear link function will be employed. The main predictor in the analyses will be group membership with *4* levels (again, collapsing across the two control conditions). Control variables in the analyses will include baseline frequency of marijuana use as well as any baseline characteristics not controlled by randomization. For these analyses we are also interested in whether baseline characteristics moderate intervention effects or if changes in TPB- and SDT-related constructs mediate the effect. Similar steps as outlined in Section D.c will be used to test these moderating and mediating effects. *Hypothesis 2c: Trends will favor the intervention conditions on days of use in the past 90 days (timeline follow-back), with a Cohen's d effect size of at least .30.*

Most studies suggest that marijuana's effects are stronger on later neurobehavioral outcomes than on birth outcomes such as birth weight. However, at least two large studies (combined N > 19,000) have found marijuana-related effects on birth weight (El Marroun et al., 2009; Fergusson, Horwood, & Northstone, 2002). We will use analyses similar to those described above in section D.d. to evaluate group-related differences in birth weight, length of hospitalization, and days in Neonatal Intensive Care. Results of these analyses will be important in informing any potential cost-related elements of the subsequent Stage II trial. In additional secondary analyses, we will also examine intervention-related effects on help seeking, and will evaluate whether group differences in marijuana use—if any—can be partially explained by differences in help seeking, especially treatment seeking. Finally, secondary analyses will examine effect size

differences for eSBIRT, texting, and combined interventions, and for the screen- vs. assessment-only control groups. Regardless of significance, any clear differences (or the lack thereof) will inform considerations of which conditions to include in Stage II.

10 SOURCE DOCUMENTS AND ACCESS TO SOURCE DATA/DOCUMENTS

Study staff will maintain appropriate medical and research records for this study, in compliance with ICH E6, Section 4.9 and regulatory and institutional requirements for the protection of confidentiality of subjects. Study staff will permit authorized representatives of NIDA and regulatory agencies to examine (and when required by applicable law, to copy) research records for the purposes of quality assurance reviews, audits, and evaluation of the study safety, progress and data validity.

Incentive Storage

Gift cards are stored in 4 main locations: a safe and a lockbox behind a locked door in the Lab, in locked file cabinet drawer in the Lab, and in a locked file cabinet at the Thea Bowman clinic (only the PC and 3 RAs have keys to it). Only 3 of each card denomination is kept in the file cabinets, to be used if participants are eligible and enroll in the study. The RAs move the gift cards to and from the UPG clinic each day there is recruitment at that clinic. The lockbox maintains approximately 5 of each card denomination for restocking purposes. The safe holds all other cards. Only the Project Coordinator has access to the safe, while the PI and PC have access to the lockbox. Electronic tracking logs are kept on Dropbox with the location of all gift cards and a detailed description of when cards change location (including date and locations before/after).

11 QUALITY CONTROL AND QUALITY ASSURANCE

The accuracy with which data input matches data output using the software was exhaustively checked prior to beginning the trial (using sample protocols). We have never found data coding errors on the part of the software in all previous trials. Although no problems are expected given past experiences with this technology, any evidence of errors in data recording by the ACASI will result in dropping all participants since the last quality check. Data will be checked once per month for out of range values and other quality issues. Data from participants collected at Hutzel Hospital will be accessible only with appropriate passwords known only to the PI and project coordinator. All biological samples will be marked with a unique subject identification number only.

The PI, the project manager, and the RA will meet regularly and review all data collection procedures, as well as recent data, to ensure that study procedures are being followed appropriately and all data are present.

12 ETHICS/PROTECTION OF HUMAN SUBJECTS

12.1 Ethical Standard

The investigator will ensure that this study is conducted in full conformity with the principles set forth in The Belmont Report: Ethical Principles and Guidelines for the Protection of Human Subjects of Research, as drafted by the US National Commission for the Protection of Human Subjects of Biomedical and Behavioral Research (April 18, 1979) and codified in 45 CFR Part 46 and/or the ICH E6.

12.2 Institutional Review Board

The Wayne State University Internal Review Board (IRB) oversees research to ensure the safe and ethical conduct of human participant research by all faculty, staff, and students of WSU. This includes reviews of proposed research, oversight committees, continuing oversight for compliance with regulations and policy, quality assurance, and education and training for investigators, staff, and committee members. The IRB is initially notified of proposed research prior to securement of funding and works with investigators to optimize study design, data collection, and associated consents and information sheets. After approval of study protocols, any changes must be submitted to the IRB via amendments. A yearly continuation is necessary so long as research is active; at this time, staff update the IRB of currently approved forms, enrollment figures, participant demographics, preliminary results (if applicable), and other pertinent information that allows the Board to determine study execution success and participant safety and protections. Upon discovering any adverse events, the Coordinator and PI are required to file a report with the IRB and perform any suggested response actions. Finally, the IRB assists staff in closing the study once data collection has been finalized.

12.3 Informed Consent Process

An informed consent information sheet will be utilized for (a) the feedback phases of this research, for both pregnant women and medical staff; and (b) as a screening consent for the pilot clinical trial. As noted in 45 CFR 46.117, part 'c:' "An IRB may waive the requirement for the investigator to obtain a signed consent form for some or all subjects if it finds...that the only record linking the subject and the research would be the consent document and the principal risk would be potential harm resulting from a breach of confidentiality." There is no need to record the participant's name in these two aspects of this particular study (intervention feedback, and clinical trial screening), and the risk from **the process of** answering questions is less than the potential harm from the results of this process being linked to a person's identity. The participant intervention feedback and pilot trial screening informed consent information sheets will be presented and reviewed by the Tablet computer. The information sheet for medical staff will be presented by a research assistant. The research assistant will review the consent document and will offer to read it aloud, and will also check for comprehension. All

informed consent information sheets will include all elements necessary for full consent, including information regarding requirements, risks, the voluntary nature of the research, and the ability to quit at any time. In all cases involving an informed consent information sheet, choosing to participate will be considered evidence of having consented. Additionally, the Tablet computer-based information sheet will utilize a "Check here if you understand and are willing to participate" button.

For the pilot randomized trial, we will utilize written informed consent for those who meet all inclusion and exclusion criteria. This consent form will be summarized by the research assistant and also read, if the participant wishes; a brief verbal quiz will check for understanding, and those failing the quiz twice will not be included in the study. The consent form will describe the nature of the two possible interventions, the kinds of questions that will be asked, the request for consent to allow limited access to their and their child's electronic medical records, follow-up procedures taking place post-partum (including being asked to give urine and hair samples to be tested for marijuana as well as cotinine, cocaine, amphetamines, barbiturates, and opiates), the participant's right to decline or guit at any time, and the possibility of distress as a result of some of the questions or material. Participants will also be told that their data will be identified by a code number only, with the only link between that code and their data being a single form kept locked in the PI's office. We have obtained a Federal Certificate of Confidentiality in order to protect participants against forced disclosure of their data; participants will be told of this additional protection, presuming our application is successful. Finally, although we will not ask any questions that might elicit reportable information in these areas, the consent form will clearly note the possible need to breach confidentiality should the investigators become aware of reportable information regarding child abuse, neglect, suicide risk, or infectious disease.

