6 STUDY PROCEDURES / EVALUATIONS

6.1 Laboratory **Procedures/Evaluations**

6.1.1 Clinical Laboratory Evaluations

Urine Results (Redwood Toxicology)

Screening Panel testing for:

Alcohol (Ethanol) 0.04 g/dL; Amphetamines 1000 ng/mL; Barbiturates 200 ng/mL; Benzodiazepines 200 ng/mL; Cocaine (Benzoylecgonine) 300 ng/mL; Cotinine (Nicotine Metabolite) 250 ng/mL; Opiates 300 ng/mL; THC (Marijuana) 50 ng/mL

Hair Results (USDTL; United States Drug Testing Laboratories, Inc.)

All categories confirmed by LC-MS/MS, with Cannabinoids tested first

AMPHETAMINES

Amphetamine 100 pg/mg; Methamphetamine 100 pg/mg; MDA 100 pg/mg; MDMA 100 pg/mg; MDEA 100 pg/mg

COCAINES

Benzoylecgonine 50 pg/mg; Norcocaine 50 pg/mg; Cocaine 100 pg/mg; Cocaethylene 50 pg/mg

OPIATES

Morphine 100 pg/mg; Oxymorphone 100 pg/mg; Hydromorphone 100 pg/mg; Codeine 100 pg/mg; Oxycodone 100 pg/mg; Hydrocodone 100 pg/mg; 6-MAM 100 pg/mg

PCP

Phencyclidine 100 pg/mg

CANNABINOIDS

Carboxy-THC GC/MS 0.05 pg/mg

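### The protocol's description of the trial consent form names six drug classes for urine and hair testing, but the laboratory panels cover nine; alcohol, benzodiazepines and PCP are not mentioned

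*Combined protocol and SAP*

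**What the plan says.** Section 12.3 (Informed Consent Process) sets out what the written consent form for the pilot randomized trial will cover. For the post-partum visit it says the woman will be asked for "urine and hair samples to be tested for marijuana as well as cotinine, cocaine, amphetamines, barbiturates, and opiates". The list has no qualifier such as 'for example' or 'other drugs', and it does not separate urine from hair.

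Section 6.1.1 (Clinical Laboratory Evaluations) gives the two panels. The urine screen begins "Alcohol (Ethanol) 0.04 g/dL; Amphetamines 1000 ng/mL; Barbiturates 200 ng/mL; Benzodiazepines 200 ng/mL" and goes on to cocaine, cotinine, opiates and THC. The hair panel has five headings: amphetamines, cocaines, opiates, PCP ("Phencyclidine 100 pg/mg") and cannabinoids. It is introduced with the line "All categories confirmed by LC-MS/MS, with Cannabinoids tested first".

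The other places that touch on testing or consent do not settle the matter:

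- Table 2 in Section 3 says only that the urine and hair samples are tested for drugs.
- The consent quiz in Section 5.2 has no item on testing.
- Section 12.3 also promises that "informed consent information sheets will include all elements necessary for full consent", but this concerns the screening and feedback phases, not the trial consent form, and it names no drug class.

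**The concern.** Section 1.3.1 identifies legal or child protective services consequences of drug use during pregnancy as the primary risk of this research. What a specimen taken at delivery could reveal is therefore material to a woman deciding whether to give it. Under Section 5.3 she may decline, and she receives an additional $25 gift card if she provides biological samples.

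Section 12.3 adds that the consent form will warn of a possible need to breach confidentiality if the investigators learn of reportable matters such as child abuse or neglect. The documents do not say how a positive alcohol, benzodiazepine or PCP result would be treated under that warning. If the form matches its description, a woman would be weighing that warning without knowing that these substances are tested.

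The documents also state no use for the three results. The objectives in Section 2 and the analyses in Section 9 draw only on the marijuana findings from the specimens.

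**Working it through.** The plan states no count of its own to reproduce, and no power or error-rate calculation is involved. The check compares two lists.

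**Inputs**

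- Described consent, Section 12.3: marijuana, cotinine, cocaine, amphetamines, barbiturates, opiates. Count 6.
- Urine panel, Section 6.1.1: alcohol, amphetamines, barbiturates, benzodiazepines, cocaine, cotinine, opiates, THC. Count 8.
- Hair panel, Section 6.1.1: amphetamines, cocaines, opiates, PCP, cannabinoids. Count 5.

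**Counting rule.** Marijuana, THC and cannabinoids are one class. Individual hair analytes are grouped under the panel's own headings, so that, for example, MDMA counts under amphetamines and oxycodone under opiates.

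**Comparison**

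| Class | Described consent | Urine | Hair |
|---|---|---|---|
| Marijuana/THC | yes | yes | yes |
| Cocaine | yes | yes | yes |
| Amphetamines | yes | yes | yes |
| Opiates | yes | yes | yes |
| Cotinine | yes | yes | no |
| Barbiturates | yes | yes | no |
| Alcohol | **no** | yes | no |
| Benzodiazepines | **no** | yes | no |
| PCP | **no** | no | yes |

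**Results**

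- Classes tested across both panels: 8 + 5 − 4 shared = 9.
- Tested but not in the described consent: 9 − 6 = 3 (alcohol, benzodiazepines, PCP).
- In the described consent but on neither panel: 0.

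**Per participant.** The follow-up checklist in Section 5.3 records agreement to urine and to hair separately, so the number depends on what a woman gives:

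- both samples: 2 + 1 = 3 unnamed classes
- urine only: 2
- hair only: 1
- neither: 0

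The hair count is an upper bound. The panel says cannabinoids are tested first, which may mean that PCP is not run on every hair sample.

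**Use of the results.** Section 9.3 uses the urine screen for 7-day marijuana use and hair analysis for 90-day marijuana use. Days of use come from the timeline follow-back interview alone. The secondary outcomes are birth outcomes, help-seeking and comparisons between conditions. None of them calls for an alcohol, benzodiazepine or PCP result.

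**The case against.** The strongest objection is that the consent form is not in the text reviewed. Section 12.3 only summarises it, inside a parenthesis about follow-up procedures, and parts of that summary read like grant-stage text: one sentence says the Certificate of Confidentiality has been obtained and also depends on the application succeeding. The form in use may name all nine classes. This stands. A reader might infer that women were not told about the three classes, but the documents show only that the described consent does not mention them.

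Nor do the two lists strictly contradict each other. Section 12.3 does not say that only those six classes are tested, and all six are on the panels. The summary is incomplete relative to the laboratory order. That too stands, but it leaves the gap unexplained, and nothing elsewhere in the protocol closes it.

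There are real safeguards. Under Section 13.2 samples carry only a non-identifying number, the laboratories receive no identifying information, and results are not available until after discharge. Section 12.5 records a Certificate of Confidentiality, and Section 1.3.1 calls the risks minimal and refers specifically to marijuana. These points lower the risk, and the documents do not show that the three extra classes measurably add to it. The safeguards protect data once collected, however; they do not replace telling a woman what will be tested.

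Lack of analytic use is also not peculiar to these three: Sections 2 and 9 do not name the cotinine, cocaine, amphetamine, barbiturate or opiate results either. This is correct. The difference is that those classes are in the described consent. Lack of use shows that dropping the three would cost the planned analyses nothing; it is not the defect itself.

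**Conclusion.** The gap is real and its size is exact on the counting rule above: six classes in the described consent, nine on the panels, three not named. At most three unnamed classes apply to a woman who gives both samples, two with urine only and one with hair only. The finding assumes that the consent form matches its description in Section 12.3 and that the panels are run as listed in Section 6.1.1.

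This is a point about consent and disclosure. Marijuana testing is in the described consent, so the 7-day and 90-day abstinence endpoints are unaffected. Days of use rest on the interview and are also unaffected.

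A reader might infer that the mismatch could lead the IRB to stop the trial. The documents do not support that. Section 3.5 ties suspension or termination to continuing or serious noncompliance, unexpected serious harm or immediate serious safety issues, and allows remedial action as an alternative to termination.

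It is still worth correcting before further samples are taken, because it bears on the trial's own stated primary risk and the correction is small.

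**What to change.** 1. Check the approved trial consent form against the urine and hair panels in Section 6.1.1. If it already names all nine classes, only the sentence in Section 12.3 needs updating.
2. If it does not, choose one of two routes before further samples are taken:
   - order panels limited to the disclosed classes, or have the laboratories report only those classes; or
   - keep the panels and add alcohol, benzodiazepines and PCP to the consent form through an IRB amendment, the route that Section 12.2 already requires for changes.
3. Make Sections 6.1.1 and 12.3 carry the same list, stating which classes are tested in urine and which in hair.
4. If samples have already been taken under a form that omits the three classes, ask the IRB how those results should be handled.

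The cost is either the loss of three results that no planned analysis uses, plus a change to the laboratory order, or a short consent amendment. Neither route alters the design, the sample size or the analysis of any endpoint.
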